SAP	Statistical Analysis Plan
SBIR	GSK Biologicals Internet Randomisation System
SD	Standard Deviation
SDTM	Study Data Tabulation Model
UL	Upper Limit of the confidence interval

1. DOCUMENT HISTORY

Date	Description	Protocol Version
1 December 2020	First Version	Amendment 1: 4 November 2020
15 July 2021	Amendment 1: Addition of elimination code 2080 in section 4.2.2.1, Addition of section 5.5 Additional analyses due to Covid-19 Pandemic, update of section 10.1.2.3.1.	Amendment 1: 4 November 2020

[figure not shown]
2. OBJECTIVES/ENDPOINTS

Objectives	Endpoints
Primary	

 To evaluate the safety and reactogenicity following intramuscular (IM) administration of RSVPreF3 OA investigational vaccine up to 1 month post-Dose 3, for all participants. 	
 Occurrence of solicited adverse events (AEs) up to 4 days post-Dose 3 (Day 4). Occurrence of unsolicited AEs up to 30 days post-Dose 3 (Day 31). Occurrence of serious adverse events (SAEs)/ Potential immune mediated diseases (pIMDs) up to 30 days post-Dose 3 (Day 31).

 To evaluate the humoral immune response following IM administration of RSVPreF3 OA investigational vaccine up to 1 month post-Dose 3, for participants vaccinated with 2 doses of RSVPreF3 OA investigational vaccine in the parent study. 	
 Humoral immune response at 1 month post-Dose 3 (Day 31) in terms of: 
 Neutralizing antibody titers against Respiratory Syncytial Virus (RSV)-A Neutralizing antibody titers against RSV-B
Secondary	

 To evaluate the humoral and cell-mediated immune (CMI) response following IM administration of RSVPreF3 OA investigational vaccine up to 1 month post-Dose 3, for participants vaccinated with 2 doses of RSVPreF3 OA investigational vaccine in the parent study. 	
 Humoral immune response at 1 month post-Dose 3 (Day 31) in terms of: 
 RSVPreF3-specific Immunoglobulin G (IgG) antibody concentrations CMI response at 1 month post-Dose 3: 
 Frequency of RSVPreF3-specific CD4+ T-cells identified as expressing at least 2 markers among IL-2, CD40L, TNF-α, IFN-γ

 To evaluate the safety and reactogenicity following IM administration of RSVPreF3 OA investigational vaccine up to the study end, for all participants. 	
 Occurrence of SAEs from vaccination (Day 1) up to study end (Month 6). Occurrence of pIMDs from vaccination (Day 1) up to study end (Month 6).
Tertiary	

 To further characterize immune responses following IM administration of RSVPreF3 OA investigational vaccine up to 1 month post-Dose 3, for participants vaccinated with 2 doses of RSVPreF3 OA investigational vaccine in the parent study. 	
 Any further exploratory immunology such as, but not limited to: 
 Antibodies against specific protein F epitopes. Potential new immunological markers for protection. Frequency of RSVPreF3-specific CD4+ and/or CD8+ T cells expressing one or any combination of immune marker(s) in vitro.

3. STUDY DESIGN

3.1. Overall design

Figure 1 Study design overview

= Vaccination with one of 9 RSVPreF3 OA investigational vaccine formulations or placebo, in RSV OA=ADJ-002 study

= Vaccination of all study participants with RSVPreF3 OA investigational vaccine in current study

N = number of participants; BS S = Blood sample for safety (hematology/biochemistry); BS H = blood sample for humoral immune responses; BS C = blood sample for CMI response
AE = adverse event; SAE = serious adverse event; pIMD = potential immune mediated disease

*Visit 1 (Day 1) = 18 months post-Dose 2 in RSV OA=ADJ-002 study

**Only for the 120-AS01E_B group that received the same, selected formulation of RSVPreF3 OA investigational vaccine in RSV OA=ADJ-002 study

CONFIDENTIAL

213569 (RSV OA=ADJ-011 EXT:002 MTH20)

Statistical Analysis Plan Amendment 1

- **Type of study:** Extension of study RSV OA=ADJ-002 (208851)
- **Experimental design:** Phase 2b, open-label, multi-center study with 3 parallel groups.
- **Duration:** Approximately 6 months per participant.
- **Primary completion date:** One month post-vaccination , i.e., Day 31 (Visit 2)
- **Control:** None
- **Blinding:** Open-label study
- **Data collection:** electronic case report form (eCRF)
- **Study groups:** refer to [Figure 1](#) for an overview of the study groups.
- Group description for analysis

The following group names will be used in the TFLs

Group order in tables	Group label in tables	Group definition for footnote
1	120-AS01E_B	Participants receiving 120 mcg RSVPreF3/AS01E after having received 2 doses of 120 mcg RSVPreF3/AS01E in parent study
2	30-AS01E_B	Participants receiving 120 mcg RSVPreF3/AS01E after having received 2 doses of 30 mcg RSVPreF3/AS01E in parent study
3	60-AS01E_B	Participants receiving 120 mcg RSVPreF3/AS01E after having received 2 doses of 60 mcg RSVPreF3/AS01E in parent study

For the analysis by age category, the following sub-group names will be used in the TFLs

Sub-group order in tables	Sub-group label in tables	Sub-group definition for footnote
1	60-69Y	60-69 years old participants at dose 1 in parent study
2	70-80Y	70-80 years old participants at dose 1 in parent study

4. ANALYSIS SETS

4.1. Definition

Table 1 Populations for analyses

Analysis Set	Description
Enrolled	Participants who agreed to participate in the clinical study after completion of the informed consent process.
Exposed	All participants who received Dose 3 of the study intervention.
Per Protocol	All participants who received Dose 3 of the study intervention and have post-vaccination data minus participants with protocol deviations that lead to exclusion.

The primary analysis for immunogenicity will be performed for the 120-AS01E_B group on the Per Protocol set (PPS) for immunogenicity. If the percentage of participants with serological results excluded from the PPS for immunogenicity for the 120-AS01E_B group is at least 10%, a second analysis will be performed on the Exposed Set (ES).

4.2. Criteria for eliminating data from Analysis Sets

4.2.1. Elimination from Exposed Set (ES)

Code 1030 (Study intervention not administered at all in the 011 study), 800 (Fraudulent data) and code 900 (invalid informed consent) will be used for identifying participants eliminated from ES

4.2.2. Elimination from Per-protocol analysis Set (PPS)

For output related to the 011 study only, the PPS as defined below will be applicable. For selected output (e.g. where data from the parent study 002 are shown together with 011 data), a combined PPS, based on the 002 and 011 PPS will be applicable. In the latter case, participants eliminated from the PPS during 002 will also be eliminated from the 011 PPS (even if not eliminated when considering only 011 output).

4.2.2.1. Excluded participants

A participant will be excluded from the PPS analysis under the following conditions.

For codes 1040, 1070, 1080, 1090, 2010, 2040, 2060, 2080: participants will be eliminated from the time at which the condition is met onwards.

For codes 2090, 2100, 2120: participants will be eliminated at the specific visit at which the condition is met.

When applicable, codes will be allocated to participants as long as they are included in the study.

CONFIDENTIAL

213569 (RSV OA=ADJ-011 EXT:002 MTH20)

Statistical Analysis Plan Amendment 1

Code	Condition under which the code is used	Visit (timepoints) where the code is applicable	Applicable for analysis
800	Fraudulent data	All	ES and PPS for analysis of immunogenicity
900	Invalid informed consent	All	ES and PPS for analysis of immunogenicity
1030	Study intervention not administered at all	All	ES and PPS for analysis of immunogenicity
1040	Administration of concomitant vaccine(s) forbidden in the protocol 
Any investigational or non-registered vaccine other than the study vaccine used during the study period beginning 30 days before the dose of study vaccine.Administration of a vaccine not foreseen by the study protocol in the period starting 30 days before and ending 30 days after the dose of study vaccine administration, with the exception of inactivated, split virion and subunit influenza vaccines which can be administered up to 14 days before or from 14 days after the study vaccination.	All	PPS for analysis of immunogenicity
1070	Vaccine administration not according to protocol 
Participant was vaccinated with the correct vaccine but containing a lower volumeRoute of the study intervention is not intramuscularWrong reconstitution of administered vaccine	Day 1	PPS for analysis of immunogenicity

CONFIDENTIAL

213569 (RSV OA=ADJ-011 EXT:002 MTH20)

Statistical Analysis Plan Amendment 1

Code	Condition under which the code is used	Visit (timepoints) where the code is applicable	Applicable for analysis
1080	Vaccine administration after a Temperature deviation 
Vaccine administered despite a Good Manufacturing Practices (GMP) no-go temperature deviation	Day 1	PPS for analysis of immunogenicity
1090	Vaccine administration after expiration	Day 1	PPS for analysis of immunogenicity
2010	Protocol violation (inclusion/exclusion criteria)	All	PPS for analysis of immunogenicity
2040	Administration of any medication forbidden by the protocol 
Any investigational or non-registered medication or medical device used during the study period beginning 30 days before the dose of study vaccineImmunosuppressants or other immune-modifying drugs administered chronically (i.e., more than 14 consecutive days in total) during the period starting 90 days prior to the vaccine doseLong-acting immune-modifying drugs administered at any time during the study periodImmunoglobulins and/or any blood products or plasma derivatives administered during the period starting 90 days before the dose of study vaccine	Day 1, Day 31	PPS for analysis of immunogenicity

CONFIDENTIAL

213569 (RSV OA=ADJ-011 EXT:002 MTH20)

Statistical Analysis Plan Amendment 1

Code	Condition under which the code is used	Visit (timepoints) where the code is applicable	Applicable for analysis
2060	
Intercurrent medical condition
 
 Participants may be eliminated from the PPS for immunogenicity if, during the study, they incur a condition that has the capability of altering their immune response (intercurrent medical condition) or are confirmed to have an alteration of their initial immune status (other than RSV infection) 	Day 1, Day 31	PPS for analysis of immunogenicity
2080	
Participants did not comply with dosing schedule
 
 Number of days between dose 2 in the parent study RSV OA=ADJ-002 and dose 3 in current study is outside [510-570 days] 	Day 1	PPS for analysis of immunogenicity
2090	
Participants did not comply with blood sample schedule
 
 Number of days between vaccination at Day 1 and Day 31 blood sample is outside [30-42 days] 	Day 31	PPS for analysis of immunogenicity
2100	
Serological results not available post-dose
 
 No immunological result at visit 2 for all the following tests: RSV A/B Neutralizing antibody titer, RSVPref3-specific IgG antibody concentration and RSVPref3-specific CD4+ T cells frequency 	Day 31	PPS for analysis of immunogenicity
2120	
Obvious incoherence or abnormality or error in data
 
 Unreliable released data as a result of confirmed sample mismatch or confirmed inappropriate sample handling at laboratory 	Day 1, 31	PPS for analysis of immunogenicity

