5.2.2. Prior/Concomitant therapy (Amended 4 November 2020)

- Use of any investigational or non-registered product (drug, vaccine or medical device) other than the study vaccine during the period beginning 30 days before the dose of study vaccine, or planned use during the study period.
- Planned or actual administration of a vaccine not foreseen by the study protocol in the period starting 30 days before and ending 30 days after the dose of study vaccine administration, with the exception of inactivated, split virion and subunit influenza vaccines which can be administered up to 14 days before or from 30 days after the study vaccination.

*Note: In case an emergency mass vaccination for an unforeseen public health threat (e.g.: a pandemic) is recommended and/or organized by the public health authorities, outside the routine immunization program, the time period described above can be reduced if necessary for that vaccine provided it is used according to the local governmental recommendations and provided **that the Sponsor is notified accordingly.***

- Administration of long-acting immune-modifying drugs or planned administration at any time during the study period (e.g. *infliximab*).
- Administration of immunoglobulins and/or any blood products or plasma derivatives during the period starting 90 days before the dose of study vaccine or planned administration during the study period.
- Chronic administration (defined as more than 14 consecutive days in total) of immunosuppressants or other immune-modifying drugs during the period starting 90 days prior to the vaccine dose or planned administration during the study period. For corticosteroids, this will mean prednisone ≥ 20 mg/day, or equivalent. Inhaled and topical steroids are allowed.
- Confirmed use or anticipated use of immunosuppressive/cytotoxic therapy (e.g., medication used during cancer chemotherapy, organ transplantation, or to treat autoimmune disorders).

CONFIDENTIAL213569 (RSV OA=ADJ-011 EXT:002 MTH20)
Protocol Amendment 1 Final**5.2.3. Prior/Concurrent clinical study experience**

- Concurrently participating in another clinical study, at any time during the study period, in which the participant has been or will be exposed to an investigational or a non-investigational vaccine/product (pharmaceutical product or invasive medical device). Refer to the [Glossary of terms](#) for the definition of invasive medical device.

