6.5. Concomitant therapy

At each study visit/contact, the investigator or delegate should question the participant about any medications/products taken and vaccinations received by the participant.

The following concomitant medication(s)/product(s)/vaccine(s) must be recorded in the eCRF:

- All concomitant medications/products/vaccines, except vitamins and dietary supplements, administered during the 30-day period following vaccination (Day 1 to Day 31).
- Any concomitant medications/products/vaccines leading to study participation/intervention non-eligibility, or an elimination from the analysis (refer to Section 5.2.2 for details).
- Any prophylactic medication (e.g. analgesics, antipyretics) administered on the day of study vaccination (Day 1) and in the absence of ANY symptom and in anticipation of a reaction to the vaccination.
- Any concomitant medications/products/vaccines relevant to an SAE/pIMD to be reported as per protocol or administered at any time during the study period for the treatment of an SAE/pIMD. Concomitant medications relevant to SAEs and pIMDs must be recorded on the Expedited Adverse Event Report.
- *Shingrix* or any AS01-containing vaccine throughout the entire study.

CONFIDENTIAL213569 (RSV OA=ADJ-011 EXT:002 MTH20)
Protocol Amendment 1 Final

The Local Medical Lead (LML) should be contacted if there are any questions regarding concomitant or prior therapy.

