9.2. Sample size determination

No sample size is calculated for this study. Potentially eligible participants who received 2 doses of the RSVPreF3 OA investigational vaccine and formulations with matched adjuvant in part B of the parent study RSV OA=ADJ-002: recombinant antigen doses 120 µg, 30 µg and 60 µg adjuvanted with AS01_E will be invited to participate in this extension study. An estimate of the maximum number of participants to be potentially enrolled can therefore be obtained by considering all currently enrolled participants in study RSV OA=ADJ-002 who received both doses in the groups considered for this extension study.

Withdrawals will not be replaced.

CONFIDENTIAL213569 (RSV OA=ADJ-011 EXT:002 MTH20)
Protocol Amendment 1 Final**9.3. Populations for analyses****Table 13 Populations for analyses**

Analysis Set	Description
Enrolled	Participants who agreed to participate in the clinical study after completion of the informed consent process.
Exposed	All participants who received Dose 3 of the study intervention.
Per Protocol	All participants who received Dose 3 of the study intervention and have post-vaccination data minus participants with protocol deviations that lead to exclusion.

The primary analysis for immunogenicity will be performed on the Per Protocol set (PPS) for immunogenicity. If in any study group the percentage of participants with serological results excluded from the PPS for immunogenicity is at least 10%, a second analysis will be performed on the Exposed Set (ES).

9.3.1. Criteria for elimination from analysis**9.3.1.1. Intercurrent medical conditions and concomitant medications/products/vaccines that may lead to elimination of a participant from per-protocol analyses**

If the participant meets one of the criteria mentioned in the Sections [5.2.1](#) (medical conditions) or [5.2.2](#) (prior/concomitant therapy), he/she may be eliminated from per protocol analysis. Refer to [Glossary of terms](#) for the definition of intercurrent medical conditions.

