9.4. Statistical analyses

The statistical analysis plan (SAP) will be finalized prior to First Participant First Visit and it will include a more technical and detailed description of the statistical analyses described in this section. This section is a summary of the planned statistical analyses of the most important endpoints including primary and key secondary endpoints.

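### SAP code 1040 exempts influenza vaccine from 14 days after the dose, but the protocol forbids it until 30 days, so the per-protocol rule for the Day 31 titres is inconsistent

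*SAP*

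**What the plan says.** Protocol 5.2.2 bars any vaccine outside the protocol from 30 days before to 30 days after the study dose. It makes an exception for inactivated, split virion and subunit influenza vaccines, "which can be administered up to 14 days before or from 30 days after the study vaccination".

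SAP 4.2.2.1 turns this into elimination code 1040, headed "Administration of concomitant vaccine(s) forbidden in the protocol". Its second bullet follows the protocol sentence, but the influenza exception reads "which can be administered up to 14 days before or from 14 days after the study vaccination". The first SAP version (1 December 2020) and SAP Amendment 1 (15 July 2021) carry the same figure. Both name Protocol Amendment 1, which has the 30-day figure, as their basis. The SAP document history shows that this section was revised in the meantime: "Addition of elimination code 2080 in section 4.2.2.1".

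Three other provisions bear on the point:

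- Code 2010 in the same SAP table eliminates from the PPS for breaches of the inclusion or exclusion criteria, at all visits. The current SAP applies it from the time the condition is met.
- Protocol 9.3.1.1 says of a participant who meets a 5.2.1 or 5.2.2 criterion that "he/she may be eliminated from per protocol analysis".
- Code 2090 accepts the Day 31 blood sample at 30 to 42 days after vaccination.

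**The concern.** The heading of code 1040 defers to the protocol, while its bullet states a different limit. For influenza vaccine given 14 to 29 days after the dose, a programmer who follows the heading removes the participant and one who follows the bullet does not. A third, who applies code 2010 because 5.2.2 is an exclusion criterion, may remove the participant anyway.

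The Day 31 RSV-A and RSV-B neutralising titres are primary endpoints. They are analysed on this PPS in one group of about 100 participants. PPS exclusions also count towards the 10% trigger for a second analysis on the Exposed Set (SAP 4.1). If the conflict is found only when a case turns up, membership would be decided in an open-label study with data in hand. The gain from a fix is that the rule is settled beforehand.

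**Working it through.** **Step 1. The two rules side by side** (influenza vaccine; days counted from the study dose)

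| Time of influenza vaccination | Protocol 5.2.2 | SAP code 1040 bullet |
|---|---|---|
| 14 days or more before | allowed | not eliminated |
| fewer than 14 days before, up to 13 days after | forbidden | eliminated |
| 14 to 29 days after | **forbidden** | **not eliminated** |
| 30 days or more after | allowed | not eliminated |

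Only the third row disagrees. Its width is 29 − 14 + 1 = 16 days.

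**Step 2. Position relative to the primary sample.** The sample is accepted at 30 to 42 days. The shortest gap from such a vaccination to the sample is 30 − 29 = 1 day, and the longest is 42 − 14 = 28 days. Every vaccination in the window precedes an accepted Day 31 sample.

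**Step 3. Does another code settle it?** Code 2010 gives no detail on vaccines after the dose.

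- For applying it: 5.2.2 is an exclusion criterion that covers actual as well as planned administration, and the code runs from the time the condition is met.
- Against: Protocol 5.2 has the criteria checked at study entry, and the specific vaccine code exempts the case.

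The text does not decide between these readings.

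**Step 4. Possible size.** The documents give no count of affected participants, no titre difference and no SD. The following are assumptions:

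- k = 0 to 3 participants affected (each one a breach of 5.2.2)
- n = 80 to 100 analysed, including the k
- d = 0.1 to 0.3, the log10 titre difference between affected and other participants, in either direction
- SD of log10 titre 0.3 to 0.5

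Ratio of the Day 31 geometric mean titre (GMT) with them kept to that with them removed: 10^(k × d / n).

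| k | n = 100, d = 0.1 | n = 100, d = 0.3 | n = 80, d = 0.1 | n = 80, d = 0.3 |
|---|---|---|---|---|
| 0 | 1 | 1 | 1 | 1 |
| 1 | 1.002 | 1.007 | 1.003 | 1.009 |
| 2 | 1.005 | 1.014 | 1.006 | 1.017 |
| 3 | 1.007 | 1.021 | 1.009 | 1.026 |

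For example, k = 3, d = 0.3, n = 80 gives 10^(0.9/80) = 10^0.01125 = 1.026. With the opposite sign it is 0.974.

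The factor from the GMT to either 95% confidence limit is 10^(t × SD / √n):

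- n = 100: 1.147 (SD 0.3) to 1.257 (SD 0.5)
- n = 80: 1.166 (SD 0.3) to 1.292 (SD 0.5)

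The largest assumed shift, 2.6%, is well inside the narrowest of these, 14.7%.

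**The case against.** The strongest defence is that the SAP is entitled to set the rule. Protocol 9.3.1.1 is permissive, and Protocol 9.4 says of the SAP that "it will include a more technical and detailed description of the statistical analyses described in this section". On that view, 14 days is an explicit number held through both SAP versions, and the protocol does not require elimination at 14 to 29 days. This stands as far as it goes: the SAP may use a narrower rule. It does not explain why a code headed as covering what the protocol forbids misstates what the protocol forbids.

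The protocol's 30 may itself be the slip. The general ban already ends 30 days after the dose, so an exception starting at 30 days relieves at most day 30 itself. A shorter interval would give the exception some content. This also stands, and the documents do not show which figure was meant. Sites, however, follow the protocol, and its Amendment 1 revised 5.2.2 while retaining 30.

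Three stronger readings are tempting but not supported:

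- *These participants stay in the PPS.* A reader might infer this from the bullet. Code 1040 only withholds one ground for elimination, and code 2010 may supply another.
- *SAP section 8 hides a departure by reading N/A.* That section covers changes to the protocol-defined analysis. The protocol's statistical section leaves the list of eliminating deviations to the SAP, so N/A is defensible.
- *Protocol 6.5 requires elimination.* It refers to elimination in connection with 5.2.2, but it is a rule on what to record in the eCRF.

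**Conclusion.** The inconsistency is real, in current text, and minor. For influenza vaccination 14 to 29 days after the dose, code 1040 contradicts both its own heading and Protocol 5.2.2, and code 2010 may give the opposite answer for the same participant. PPS membership for the primary Day 31 titres is therefore not fixed for these cases.

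The 16-day window and the 1 to 28 day gap follow from the documents. The effect on the result does not. Under the stated assumptions the Day 31 GMT changes by 0% with no one affected, 0.2 to 0.9% with one, and 0.7 to 2.6% with three. Neither document says that influenza vaccine alters RSV titres. The number affected is unknown and may be zero. The study is descriptive, and safety is analysed on the Exposed Set, which code 1040 does not touch. Nothing here shows that a conclusion would change.

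**What to change.** Before the PPS is derived, change the post-dose figure in the influenza exception of code 1040 from 14 to 30 days. This matches the protocol that sites follow, and codes 1040 and 2010 can then no longer disagree on these vaccinations.

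If the sponsor confirms that 14 days was intended for the PPS, keep it, say explicitly that it is shorter than the limit in Protocol 5.2.2, and state that code 2010 does not apply to influenza vaccination 14 to 29 days after the dose.

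The cost is one number in one SAP row, or a sentence or two of SAP text. Protocol 6.5 already has vaccines given from Day 1 to Day 31 recorded in the eCRF, so neither option needs new data, a protocol amendment or an extra analysis.

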9.4.1.2. Immunogenicity

- Any missing or non-evaluable immunogenicity measurement will not be replaced. The descriptive analysis performed for each assay at each time point will exclude participants with a missing or non-evaluable measurement.
- The geometric mean titers/concentrations (GMTs/GMCs) will be computed by taking the anti-logarithm of the arithmetic mean of the \log_{10} transformed titers/concentrations.

CONFIDENTIAL213569 (RSV OA=ADJ-011 EXT:002 MTH20)
Protocol Amendment 1 Final

- A seronegative participant will be defined as a participant whose antibody titer/concentration is below the cut-off value of the assay. A seropositive participant is a participant whose antibody titer/concentration is greater than or equal to the cut-off value of the assay.
- Antibody titers/concentrations below the assay cut-off will be given an arbitrary value of half the assay cut-off for the purpose of GMT/GMC calculation.
- Antibody titers/concentrations above the assay upper limit of quantification (ULOQ) will be given the value of the ULOQ for the purpose of GMT/GMC calculation.

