8. CHANGES TO THE PROTOCOL DEFINED STATISTICAL ANALYSIS

N/A

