10.1.2.2. Laboratory data

Missing laboratory results (including immunological data) will not be replaced.

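### SAP code 2120 removes the whole visit from the immunogenicity per-protocol set when one sample is unreliable, and no rule clearly removes that unreliable result from the Exposed Set

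*SAP*

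**What the plan says.** Code 2120 in SAP 4.2.2.1 covers "Unreliable released data as a result of confirmed sample mismatch or confirmed inappropriate sample handling at laboratory". It applies at Day 1 and Day 31, and the table assigns it to the immunogenicity PPS only. The text above the table sets the level of removal: "For codes 2090, 2100, 2120: participants will be eliminated at the specific visit at which the condition is met". Nothing limits the removal to the sample or assay at fault.

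Code 2100, in the same table, removes the Day 31 visit only when neutralization, IgG and CD4+ T-cell results are all absent.

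For the ES, SAP 4.2.1 names codes 1030, 800 and 900 and says that these "will be used for identifying participants eliminated from ES". Code 2120 is not among them. SAP 4.1 calls for a second immunogenicity analysis on the ES if at least 10% of 120-AS01E_B participants with serology are excluded from the PPS.

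Protocol 9.4.1.2 has a rule at the level of the result: "The descriptive analysis performed for each assay at each time point will exclude participants with a missing or non-evaluable measurement". It is not tied to one analysis set. SAP section 8, where departures from the protocol analysis would be declared, reads N/A.

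**The concern.** Serum and PBMC come from separate draws and are processed differently, so a laboratory error can affect one and leave the other sound. If the cell-mediated sample is mishandled but its result has been released, the literal rule takes the participant's serum titers out of the primary immunogenicity analysis for a reason unrelated to the serum. Had the same PBMC result never been produced, code 2100 would have kept those titers. The SAP gives no reason for treating the two cases differently.

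There is also a gap on the ES side. That analysis is the check on the PPS result when exclusions are frequent, so a value confirmed as wrong should not contribute to it. The SAP does not say that it is removed. At stake are some precision in the primary titers and the cleanliness of a conditional sensitivity analysis.

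**Working it through.** **Inputs from the documents**
- Size of the immunogenicity group, 120-AS01E_B: about 100 (Protocol Table 4).
- Separate samples: about 20 mL for humoral and 25 mL for cell-mediated response at each of two visits (Protocol Table 7). Check: 2 × (20 + 25) = 90 mL, which matches the stated total.
- ES trigger: at least 10% excluded (SAP 4.1), so 10 participants out of 100, over all PPS codes together.
- Rates of mishandling or mismatch, and the expected fold rise: not given. The ranges below are assumptions.

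**Rules side by side for a Day 31 visit with sound serum**

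| PBMC result | Rule | Serum titers in PPS |
|---|---|---|
| Missing | 2100 (all tests must be absent) | kept |
| Released, then confirmed unreliable | 2120 (participant removed at the visit) | removed, read as written |
| Non-evaluable | Protocol 9.4.1.2 (by assay and time point) | kept |

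**Precision lost if k sound titers out of 100 are dropped**

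Ratio of log-scale 95% interval half-widths = [t(0.975, 99−k)/√(100−k)] ÷ [t(0.975, 99)/√100]. The denominator is 1.9842/10 = 0.19842.
- k = 2: (1.9847/√98) ÷ 0.19842 = 1.0104, about 1% wider.
- k = 5: (1.9855/√95) ÷ 0.19842 = 1.0267, about 3% wider.
- k = 10: (1.9870/√90) ÷ 0.19842 = 1.0556, about 6% wider.

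The mean geometric increase (MGI) over pre-Dose 3 needs both visits, so a code at either visit loses the pair. The planned age-category analyses have fewer participants, so each loss weighs more there.

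**Whether the unreliable value is removed from the ES**
1. Code 2120 does not apply to the ES, so the participant stays in it.
2. Protocol 9.4.1.2 would drop the result from any set if it counts as non-evaluable. Neither document defines that term or says that a confirmed mismatch falls under it.
3. Code 2120 concerns released data, so a reported result exists. SAP 10.1.3.3 carries a numeric serology result between the cut-off and the upper limit of quantification through unchanged.
4. The SAP's own laboratory rule mentions only missing results: "Missing laboratory results (including immunological data) will not be replaced". The protocol counterpart also covers non-evaluable ones: "Any missing or non-evaluable immunogenicity measurement will not be replaced".

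The value's removal therefore depends on an undefined word.

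**Size if such values did stay in the ES**

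A Day 1/Day 31 swap turns a participant's log-ratio from +log F into −log F. With k swaps out of 100, the MGI is multiplied by F^(−2k/100). For an assumed F of 2 to 8:
- k = 1: 2^(−0.02) to 8^(−0.02), so 1.4% to 4.1% lower.
- k = 5: 2^(−0.10) to 8^(−0.10), so 6.7% to 18.8% lower.

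**The case against.** The strongest reply is that the rules work in layers. SAP 4.2.1 and 4.2.2.1 decide who belongs to a set; Protocol 9.4.1.2 then decides which results within it are usable. On that view there is no contradiction, and a per-protocol rule stricter than a missing-data rule is a normal, conservative choice. This stands in part: it rules out calling the texts contradictory. It does not explain why a faulty PBMC result costs the serum titers when an absent one does not.

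A reader might infer that the plan keeps confirmed mismatches in the ES analysis. The documents do not support that. The ES code list concerns participants, not values, and the protocol rule, which the SAP does not declare changed, would remove a non-evaluable result from the ES as well. What stands is that nobody has said whether such a result is non-evaluable.

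It is also fair that code 2120 states no assay scope, so whole-visit loss from one bad tube is the literal reading and not an explicit statement. The harms partly offset each other too: if exclusions reach 10%, the ES analysis brings the sound titers back. Finally, a mismatch is an error of identity. All three antibody assays use serum from the humoral draw, so keeping every other assay at the visit could retain doubtful results. That objection is sound, and the remedy has to be defined by sample.

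**Conclusion.** The point holds as a gap in specification with a wasteful literal reading. As written, code 2120 discards sound primary titers when only the PBMC sample is at fault, out of line with code 2100 and Protocol 9.4.1.2. Separately, the SAP does not itself remove a confirmed-unreliable value from the conditional ES analysis, and the protocol does so only if the value is classed as non-evaluable.

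The expected effect is small: about 1% to 3% wider log-scale intervals for 2 to 5 lost titers out of about 100. The number of such events is assumed. The swap figures are illustrations that need three things together: confirmed swaps, a failure to class them as non-evaluable, and the 10% trigger being met. The study is descriptive, with no hypothesis test, so no decision rule is affected. The case for acting is that a primary endpoint is exposed and the repair is easy.

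**What to change.** Make code 2120 a sample-level rule in SAP 4.2.2.1, for example: *All results from the affected sample(s) are treated as non-evaluable and set to missing in both the PPS and the ES; results from unaffected samples of the same participant and visit are kept.* Then remove 2120 from the list of codes that eliminate the participant at the visit. This also settles what non-evaluable means for the protocol rule.

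The cost is one SAP sentence and a small programming change, with no new data. The one downside is that the laboratory must establish which sample or samples are affected before any result from that visit is kept, which matters most for a mismatch.
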